5.8 Power and sample size analysis

We provide an approximate sample size and power calculation by providing the largest odds ratios (corresponding to the minimum detectable treatment effects, which are indicated by odds ratios less than 1, reflecting treatment benefit) which can be detected in a frequentist analysis under of the primary outcome under a proportional model without covariate adjustment. The target sample size of this trial is 300 randomized subjects; the table also considers smaller sample sizes to indicate the power the trial will reach under optimistic scenarios for controlling the COVID-19 outbreak. The power calculations were performed using statistical simulation (N=10,000 simulations per combination), and provide results very close to those provided by an approximation provided by Whitehead.²⁷ We consider three scenarios for the distribution in the azithromycin group for the 8 categories of the COVID Ordinal Outcomes Scale: Scenario 1: Uniform distribution with probabilities of 0.125 for each score level, Scenario 2: Overall probabilities at 14 days averaging across both groups of the recent COVID-19 trial by Cao et al.²⁸ (1= 0, 2= 0.36, 3=0.16, 4=0.23, 5=0.05, 6=0.02, 7=0.02, 8=0.16), and Scenario 3, with probabilities averaged between Scenarios 1 and 2.

Maximum Detectable Odds Ratios (below 1) with 80% Power, 2-sided α = 0.05, Assuming 95% Follow-up			
Sample size	Scenario 1 (uniform)	Scenario 2	Scenario 3
100	0.34	0.32	0.33
150	0.43	0.41	0.42
200	0.48	0.46	0.48
250	0.52	0.50	0.52
300	0.55	0.54	0.55

We note that when expressed as risk ratios the minimum detectable effects are closer to 1 than the odds ratios in the table. For example, in Scenario 3 with N = 300, the detectable odds ratio of 0.55 for a COVID Ordinal Outcomes Scale score > 3 translates to a detectable risk ratio of $0.702 = 0.337/0.48$. Thus the target sample size of 300 provides good power to detect an important signal for superiority of hydroxychloroquine over azithromycin. In any case, we anticipate that the data from this study can meaningfully contribute to future meta-analyses of therapeutics for COVID-19.

6.0 Human Subjects Considerations

6.1 Pandemic considerations.

The exponentially rapid spread of COVID-19 across the globe and the very high rate of contagion, especially in healthcare environments, necessitates flexibility in specific logistical details that is nevertheless robustly consistent with the ethical mandates of clinical research. The key aspects of this pragmatic trial special to the

pandemic circumstance are (1) time-sensitivity of trial launch and (2) the need for no-touch operations on the part of research staff to protect their safety. Time-sensitivity and the emotional valence of proposed therapies for a frightening pandemic infection—plus the need to rapidly evaluate a large number of proposed therapies, many of which are already entering clinical practice in advance of evidence—motivate the use of an expeditious, pragmatic, real-world, open-label, active comparator design for this evaluation of the efficacy of hydroxychloroquine. The mandate to protect research staff while assuring that informed consent is obtained drives the choice of electronic consent. “No-touch” consenting procedures will abide by Intermountain guidelines and standards for consenting in pandemic circumstances, including a HIPAA waiver as appropriate.

6.2 Institutional Review Board oversight.

Institutional Review Board (IRB) approval is required and will be secured before any subject is enrolled at the study site. IRB notices will be written and dated. The investigator will promptly report to IRB all changes in the research activity and all unanticipated problems involving risk to human subjects or others, and will not make any changes in the research without IRB approval, except where necessary to eliminate apparent immediate hazard to human subjects.

6.3 Selection of subjects.

Federal regulations at 45 CFR 46(a)(3) require the equitable selection of subjects. The sites will be evaluated to determine whether patient eligibility criteria are met, drawing on routine clinical data. No protocol-specific tests nor procedures will be performed as part of the screening process. Study exclusion criteria neither unjustly exclude classes of individuals from participation in the research nor unjustly include classes of individuals for participation in the research.

6.4 Justification for including vulnerable subjects.

The present research aims to investigate patients with COVID-19. Due to the nature of the condition, many of these patients will have impaired decision-making capabilities. Moreover, those with intact decision-making capacities likely have milder disease than those with impaired capacity, creating substantial risk of sampling bias. Therefore, this study could not be conducted if limited to enrolling only those subjects with retained decision-making capacity. Hence, subjects recruited for this trial are not being unfairly burdened with involvement in this research simply because they are easily available. They are the core group of patients most likely to experience benefit from hydroxychloroquine or azithromycin.

6.5 Informed consent.

Federal regulations at 21 CFR 50.20 and 45 CFR 46.111(a)(5) require that informed consent be sought from each prospective subject or the subject’s LAR. Each study participant or LAR must sign and date an IRB-approved informed consent form. The consent form (via a HIPAA authorization) will also indicate that protected health information (PHI) may be released to relevant study personnel and regulatory agencies.

Some of the patients approached for participation in this research protocol will be decisionally impaired due to their critical illness. Hence, some patients will not be able to provide informed consent. Accordingly, informed consent will be sought from the participant’s LAR, as defined at 45 CFR 46.102(c): “an individual or judicial or other body authorized under applicable law to consent on behalf of a prospective subject to the subject’s participation in the procedures(s) involved in the research.” In this study, LARs will be identified as stipulated by relevant regulations and statutes, as per the standards defined for clinical decision making, as is the standard practice in human subjects research.

According to a previous President’s Bioethics Committee (National Bioethics Advisory Committee (NBAC)), an investigator should accept a relative or friend of the potential subject who is recognized as an LAR for purposes of clinical decision making under the law of the state where the research takes place.²⁹ Finally, OHRP has stated in their determination letters that a surrogate could serve as a LAR for research decision

making if such an individual is authorized under applicable state law to provide consent for the “procedures” involved in the research study.³⁰

In cases of LAR consent, study personnel obtaining informed consent are responsible for ensuring that the LAR understands the risks and benefits of participating in the study, answering any questions the LAR may have throughout the study and sharing any new information in a timely manner that may be relevant to the LAR’s willingness to permit the subject’s continued participation in the trial. The study personnel obtaining consent will make every effort to minimize coercion, whether actual or perceived. All study participants or their LARs will be informed of the objectives of the study and the potential risks. The informed consent document will be used to explain the risks and benefits of study participation to the LAR in simple terms before the patient is enrolled in the study, and to document that the LAR is satisfied with his or her understanding of the risks and benefits of participating in the study and desires to participate in the study. The electronic consent form will document the receipt of informed consent.

6.6 Continuing consent.

For subjects for whom consent was initially obtained from a LAR but who subsequently regain decisional capacity while in hospital, sites will seek reconsent for continuing participation. Reconsent will also use electronic consenting methods; in the event that reconsent is not able to be obtained before 6-month followup, then consent for that telephone call will be obtained via oral consent, as the only additional study procedure at that point is a brief telephone call.

6.7 Withdrawal of consent.

Patients may withdraw or be withdrawn (by their LAR) from the study at any time. Data recorded up to the time of withdrawal will be included in the study analysis, unless consent to use data has also been withdrawn. If a patient (or LAR) requests withdrawal from the study after completion of study treatments, study endpoints will be determined unless consent to do so has also been withdrawn.

6.8 Confidentiality.

Federal regulations at 45 CFR 46.111(a)(7) require, when appropriate, adequate provisions to protect the privacy of subjects and to maintain the confidentiality of data. To maintain confidentiality, reports will be identified only by a coded study number. Only the study team will have access to the codes. All records will be kept in a locked, password protected computer. All computer entry and networking programs will access coded numbers only. All paper CRFs will be maintained in locked offices. Information shared outside Intermountain will be deidentified in accordance with federal regulations, e.g., HIPAA, except as otherwise indicated. Any data sharing will be regulated by appropriate data use agreements, where required. For the purposes of reporting, PHI may be disclosed to relevant regulatory agencies.

6.9 Protocol deviations and violations.

The investigator will not implement any deviation from, or changes of the protocol without prior review and documented approval/favorable opinion from the IRB of an amendment, except where necessary to eliminate immediate hazard(s) to study subjects, or when the change(s) involves only logistical or administrative aspects of the trial (e.g., change of telephone number(s)). Any deviation from the approved protocol will be documented and explained by the investigator or a person designated by the investigator. The investigator may implement a deviation from, or a change to, the protocol to eliminate immediate hazard(s) to trial subjects without prior IRB approval/favorable opinion. As soon as possible, the implemented deviation or change, the reasons for it, and if appropriate, the proposed protocol amendment will be submitted to the IRB.

7 Adverse Events

Patient safety is central to this study protocol.

7.1 Adverse event reporting. The following adverse events will be collected in the adverse event case report forms:

- Serious adverse events
- Nonserious adverse events that are considered by the investigator to be related to study drug or study procedures or of uncertain relationship
- Adverse events that lead to permanent discontinuation of the study drug.

A clinical trial adverse event is any untoward medical event associated with the use of a drug or study procedure in humans, whether or not it is considered related to a drug or study procedure (see Appendix 4).

After randomization, adverse events related to protocol procedures or occurring after the patient receives the first dose of study drug must be evaluated by the study investigator. If the adverse event is judged to be reportable, the investigator will report to the DSMB his/her assessment of the potential relatedness of each adverse event to study drug or study procedure. Investigators will assess whether there is a reasonable possibility that the study drug or procedure caused the event, based on the criteria outlined in Appendix 4. Investigators will also consider whether the event is unanticipated or unexplained given the patient's clinical course, previous medical conditions, and concomitant therapies.

Adverse events that will be collected prospectively as part of the study-specific outcome (and thus would not be separately reported as adverse events) are listed in Appendix 4. Study-specific outcomes will be reported as adverse events if they are both serious and Definitely or Possibly Related to study drug.

7.2 Serious Adverse Events

Serious adverse event collection begins after the patient or LAR has signed informed consent and has received study drug or undergone study procedures. If a patient experiences a serious adverse event after consent, but prior to receiving study drug, the event will NOT be collected unless the investigator feels the event may have been caused by a study procedure.

Investigators must alert the DSMB of any **serious and study drug or study procedure related** adverse event within 24 hours of investigator awareness of the event. Alerts issued via telephone are to be immediately followed with official notification on the adverse event case report form. See Appendix 4 for reporting timelines for serious, unexpected, study related events (SAEs) and serious, unexpected suspected adverse reactions (SUSARs).

As per federal definitions (primarily in 21 CFR 312.32(a)), a **serious** adverse event is any adverse event that results in one of the following outcomes:

- Death
- A life-threatening event, one that places the subject at immediate risk of death (this does not include an event that, had it been more serious, would have placed the subject at immediate risk of death)
- Prolonged inpatient hospitalization or rehospitalization
- Persistent or significant disability/incapacity, indicating a substantial disruption of a person's ability to conduct normal life functions (i.e., the adverse event resulted in a significant, persistent or permanent change, impairment, damage or disruption in the patient's body function/structure, physical activities and/or quality of life).

Important medical events that may not result in death, be life-threatening, or require hospitalization may be considered serious adverse events when, based upon appropriate medical judgment, they may jeopardize the patient and may require medical or surgical intervention to prevent one of the outcomes listed in this definition.

Serious adverse events will be collected during the first five days, regardless of the investigator's opinion of causation. Thereafter, serious adverse events are not required to be reported unless the investigator feels the events were related to study drug or a protocol procedure.

APPENDICES

Appendix 1. Visit schedule

Procedure	Visit						
	Baseline	24-48 hours post-randomization	Daily through 5 days	14 days	Hospital discharge	28 days	6 months
Screening procedures	X						
Informed consent and LAR identification	X						
Patient reconsent (where necessary)					X		
Data collection	X				X		
EKG (research or clinical)		X					
Study drug			X				
Active Adverse Event review			X				
Passive Adverse Event review					X		
WHO ordinal scale				X*			
VFD, ICUFD, HFD						X	
EQ-5D-5L							X

LAR: legally authorized representative; WHO: World Health Organization; VFD: Ventilator-free days; ICUFD: ICU-free days; HFD: hospital-free days; EQ-5D-5L: EuroQol-5 dimensions-5 level

*measured daily, days 1–7, 14 on all patients; measured days 1–14 on patients still hospitalized on day 14.

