3.6 Secondary endpoints

Hospital-free days at 28 days (calculated as a worst-rank ordinal)

Ventilator-free days at 28 days (calculated as a worst-rank ordinal)

ICU-free days at 28 days (calculated as a worst-rank ordinal)

Time to a 1-point decrease in the WHO ordinal recovery score

The composite endpoints (-free days) will be calculated according to standard procedures (using the “last off” method) and using the worst-rank ordinal approach by which death is counted as -1 days.

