Note: if the clinical attending physician believes that bacterial pneumonia is likely and requires a second antibacterial agent for "atypical" infection (an uncommon occurrence in COVID-19), patients may receive another agent (e.g., doxycycline or levofloxacin) as appropriate at the clinician's discretion.

5.2.2. Azithromycin. Patients in the azithromycin arm will receive azithromycin 500mg on day 1 plus 250mg daily on days 2-5 (may be administered IV per clinician preference).

5.3 Study Assessments. Coordinators and/or data queries will classify the COVID Ordinal Outcomes Scale on days 1–7, 14. They will also review for adverse events, including especially rash, self-report of visual changes, or symptomatic hypoglycemia. They will ensure that an EKG is performed at 24 to 48 hours post-randomization time. If a clinical EKG is not performed during this timeframe, a research EKG will be performed. In addition, ventilator status and ICU and hospital stay (using the last-off method) will be used to determine ventilator- and ICU-free days at 28 days using the worst rank ordinal technique, whereby death is scored as -1 days. In addition, coordinators and/or data queries will classify the COVID Ordinal Outcomes Scale on day 14. If this cannot be determined from the medical record, the patient will be contacted via telephone, mail, or electronic methods to determine their status on day 14.

5.2.4 Six-month assessment. A brief visit will ascertain the EQ-5D-5L to measure quality of life. Mortality and readmissions will also be assessed at that visit, which may be performed by telephone, electronic means, or in-person, depending on the subject's needs and preferences.

5.4 Approach to potential risks. Hydroxychloroquine has been used in many thousands of patients as an anti-malarial agent and in systemic lupus erythematosus and rheumatoid arthritis as a mild anti-inflammatory agent. The safety has been well established. Azithromycin has been used in millions of patients and is effective against the causes of bacterial pneumonia. Its immunomodulatory effects are also of interest in a variety of syndromes. While both agents have known side effects, such side effects are generally rare and well-tolerated.

This pragmatic study protocol is designed to optimally protect patients against risk through careful choice of exclusion criteria, pragmatic monitoring for common adverse events, and careful oversight by a DSMB.

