General. Descriptive summaries will be produced for subject disposition, demographic and clinical characteristics of the randomized hydroxychloroquine and azithromycin groups. The primary analysis and other secondary analyses of efficacy outcomes will be performed in accordance with the intention-to-treat (ITT) principle, with all patients analyzed according to their randomized treatment assignment, irrespective of compliance. In addition to the formal statistical analyses described below, the proportions of subjects with each level of the 8-point COVID scale will be displayed in frequency tables and in graphical summaries for each day, from day 0 (baseline) through day 14 of follow-up. Other ordinal secondary outcomes will generally be summarized using medians, 10th, 25th, 75th, and 90th percentiles and plots of cumulative distribution functions. In cases where a substantial proportion of subjects fall into an extreme category, several of the indicated quantiles may take on the value of this category and a quantile-based summary may not be fully informative. In these cases, we will tabulate the proportions of subjects which fall into designated categories which are defined based on clinical relevance.

Adherence to the study medications will be summarized by providing the distributions of the proportion of doses of study medication which were administered to each patient overall and by randomized group. We will compute two proportions: 1) The proportion of protocol-intended dose, in which doses for which the patient had a protocol-specified reason not to receive study medication (e.g., prolonged QTc, died, or discharged home) will not be counted in the denominator for proportion of scheduled doses received. 2) The proportion of the total ideal dose, in which doses for which the patient had a protocol-specified reason not to receive study medication will be counted. We will also describe the median (IQR) for total doses received for both protocol-intended dose and ideal dose.

Analysis Sets. The primary analysis and analyses of secondary efficacy outcomes will be performed in the ITT population, which consists of all randomized patients. Although the trial was launched with the flexibility to enroll patients with suspected rather than confirmed COVID-19, no patients were HAHPS SAP

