Secondary Analyses. We will apply similar Bayesian proportional odds models to evaluate the effectiveness of the hydroxychloroquine vs. azithromycin interventions for efficacy analyses of all ordinal outcomes. We will also present numbers (proportions) of patients in each ordinal status for all endpoints for descriptive purposes and to assist with future meta analyses. If the graphical diagnostics (described above) indicate that the proportional odds model is untenable for certain outcomes, we will report that fact, and supplement the primary analysis using the proportional odds model with separate logistic regression for different cutpoints or quantile regression in order to fully characterize the relationship of each outcome with treatment assignment.

Ordinal secondary outcomes include ventilator-, ICU-, and hospital-free days through day 28 (with death assigned as a worst-rank ordinal level^{5,6} to avoid survivorship bias for each of these outcomes). We will use the last-off method—only time after the last liberation from, e.g., ventilation counts toward the total number of -free days. Similar to the primary outcome measured at 14 days, we will apply a primary proportional odds model similar to that used for the primary analysis at day 14 to evaluate the effect of the randomized treatments on the COVID Ordinal Outcomes Scale at day 7. We will present the results of each of these analyses as the posterior median odds ratio with 95% credible interval under the moderately skeptical Bayesian prior described above. For ease of use for investigators performing meta-analyses, we will include detailed descriptions including number of patients for each value of the endpoints by treatment group as tables in the online supplement.

We include two time-to-event endpoints, censored at 28 days: time to a 1-point decrease in the COVID Ordinal scale and time to recovery (defined as in the ACTT-1 trial). The time to recovery endpoint was added after publication of the methods paper but before unblinding of investigators. It was added to assist with future meta analyses given increasing interest in it as an endpoint. Both time-to-event endpoints will be displayed by treatment group (for descriptive purposes) as Kaplan-HAHPs SAP

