Meier curves. Patients who die prior to day 28 are assigned an artificial follow-up time of 28 days censored at that point. This will assign to these patients a worse outcome than any surviving patients, and avoid conflating prolonged hospitalization with death. Descriptively, these time-to-event endpoints will be displayed as median (IQR). If fewer than half of patients meet the event before censoring, we will choose an appropriate quantile (e.g., first quartile) for description and display the proportions with events during the respective weeks of follow-up. For the sake of consistency, we will use the same ordinal regression model with the same prior distribution for the odds ratio as was used for the primary analysis to generate median posterior odds ratios and credible intervals for these endpoints.

Sub-groups. On a purely exploratory level, we will summarize effect variation in sub-groups defined by (a) age \geq 65 years, (b) symptom duration \geq 10 days, (c) in ICU at enrollment, (d) presence of at least one comorbidity, (e) race/ethnicity, and (f) receipt of any clinical azithromycin before enrollment. At early interim analyses, the sample size will be too small to support meaningful statistical inference, and we will limit presentation of results in sub-groups to descriptive summaries using the summary measures described for each outcome above.

Missing Data. We expect fewer than 5% of subjects will have missing data on either the primary or key secondary outcomes listed above. Hence, our primary analyses will be restricted to non-missing observations, without imputation. For the primary outcome, a sensitivity analysis will be performed by applying single imputation. Where daily COVID Ordinal Outcomes Scale scores are missing after hospital discharge, we will use last carried forward with the following modifications—patients discharged to a facility other than home will be classified as “home with limitations” (score 2), and patients found subsequently to be home with limitations will be rated as “home with limitations” from hospital discharge through that follow-up point. Patients who are discharged to home and found to have no limitations at day 14 will be rated as “home without” limitations starting at the time of hospital HAHPS SAP

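### No ordinal score is scheduled from day 8 to exit for inpatients who leave or die before day 14, leaving gaps in the daily displays and dating some improvements late

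*Protocol*

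**What the plan says.** **Collection.** Protocol section 5.3 says that coordinators or data queries "will classify the COVID Ordinal Outcomes Scale on days 1–7, 14"; it does not mention days 8–13. The footnote to Protocol Appendix 1 gives the same days for everyone ("measured daily, days 1–7, 14 on all patients") and then adds a second group: "measured days 1–14 on patients still hospitalized on day 14".

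**Use.** The SAP, under General, commits to frequency tables and "graphical summaries for each day, from day 0 (baseline) through day 14 of follow-up"; Protocol section 5.7 makes the same commitment. Protocol section 3.6 lists as a secondary endpoint "Time to a 1-point decrease in the WHO ordinal recovery score". The SAP, under Secondary Analyses, says "We include two time-to-event endpoints, censored at 28 days: time to a 1-point decrease in the COVID Ordinal scale and time to recovery".

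**Filling rules.** The SAP's Missing Data section has one rule for daily scores. It begins "Where daily COVID Ordinal Outcomes Scale scores are missing after hospital discharge" and carries the last value forward, with adjustments for discharge to a facility and for status found at follow-up. Under Secondary Analyses, patients who die before day 28 get a 28-day censored time in the time-to-event endpoints.

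**The concern.** The two collection statements disagree with each other, and neither supplies what the analyses need. Under section 5.3 nobody is scored on days 8–13. Under Appendix 1, whether a day-9 score exists depends on where the patient is on day 14. Being in hospital on day 14 means levels 3–7 of the primary outcome scale (Protocol Table 1), so measurement on days 8–13 is conditional on a later outcome.

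Two products are at stake. The daily displays for days 8–13 would lack the in-hospital states of patients about to go home or about to die. The time to a 1-point decrease would be dated differently for patients with the same clinical course up to the date of improvement. The SAP analyses this endpoint with the ordinal regression model, so a late date moves the patient's rank.

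**Working it through.** The documents state no figure for days 8–13 coverage, so there is none to reproduce. The check sets the schedule against the analyses and then bounds the share affected.

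**Step 1. Two patients under Appendix 1.** Both start at level 5, stay there through day 8, and are at level 4 from day 9.

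| | Discharged day 12 | Still in hospital day 14 |
|---|---|---|
| Days 1–7 | scored | scored |
| Day 8 to exit | days 8–12 not scheduled | scored |
| After exit | SAP post-discharge rule | not applicable |
| Day 14 | scored | scored |
| True first 1-point decrease | day 9 | day 9 |
| Earliest date the data support | day 12 (discharge) | day 9 |

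The first patient is dated 12 − 9 = 3 days late. The largest delay from this mechanism is an improvement on day 8 with discharge on day 13: 13 − 8 = 5 days. Scoring each calendar day by its worst status (Protocol Table 1 footnote) could push the first ambulatory score one day further, hence *about* 5.

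**Step 2. Upper bound on the share with unscored inpatient days.** The inputs are the azithromycin day-14 distributions in Protocol section 5.8, repeated in the SAP's Sample size and power section. The share in hospital on day 14 is P(levels 3–7).

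- Scenario 1: 5 × 0.125 = 0.625
- Scenario 2: 0.16 + 0.23 + 0.05 + 0.02 + 0.02 = 0.48
- Scenario 3: (0.625 + 0.48) / 2 = 0.5525

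The complements, with no days 8–13 score scheduled, are 0.375, 0.52 and 0.4475. If these applied to all 300 patients, that would be about 113, 156 and 134. These are upper bounds under Appendix 1, because they include everyone who left or died before day 8. Under section 5.3 alone, patients still in hospital on day 14 are unscored too.

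**Step 3. Range for the displays.** The share of exits falling on days 9–13 is not in the documents. Assuming 25%, 50% or 75% of all exits by day 14:

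- Scenario 1: 0.375 × (0.25, 0.50, 0.75) = 9%, 19%, 28%
- Scenario 2: 0.52 × (0.25, 0.50, 0.75) = 13%, 26%, 39%
- Scenario 3: 0.4475 × (0.25, 0.50, 0.75) = 11%, 22%, 34%

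The full range is 0 to 52% in Scenario 2.

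**Step 4. Tighter bound for time to a 1-point decrease.** Deaths before day 28 are censored at day 28 whatever happened earlier, so remove level 8:

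- Scenario 1: 0.375 − 0.125 = 0.25
- Scenario 2: 0.52 − 0.16 = 0.36
- Scenario 3: 0.4475 − 0.1425 = 0.305

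Still to be removed, in unknown numbers, are survivors discharged by day 8, those already improved by day 7, and those at baseline level 3, whose first decrease is discharge itself.

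**Step 5. Can scheduled measurement differ by arm?** Take Scenario 2 and the SAP's detectable odds ratio of 0.55 at N = 300.

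- P(score > 2) on azithromycin is 0.64. The odds are 0.64/0.36 = 1.778; × 0.55 = 0.978, giving 0.494.
- P(death) on azithromycin is 0.16. The odds are 0.190; × 0.55 = 0.105, giving 0.095.
- In hospital on day 14 on hydroxychloroquine: 0.494 − 0.095 = 0.40, against 0.48 on azithromycin.

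Scored shares can therefore differ by arm. This does not give the direction or size of any bias in event times.

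**Step 6. Beyond day 14.** The improvement endpoint is censored at day 28, but neither schedule lists the scale on any of days 15–28. In-hospital improvements after day 14 have the same dating problem, including those of patients scored daily through day 14.

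**The case against.** The strongest reply is that much of days 8–13 can be filled. The SAP rule supplies scores after discharge, death fixes level 8, and a discharge date itself dates a drop to level 2 or below. A reader might infer from the footnote that everything shown for days 8–13 comes from patients still in hospital on day 14. The documents do not support that. Patients who left before day 8 can be placed on all those days, and later leavers from their exit onward. This part of the objection stands and narrows the gap to the inpatient days from day 8 to exit. One caveat is that the rule follows directly on the single-imputation sensitivity analysis for the primary outcome. The SAP does not say whether it also governs the daily displays or the time-to-event endpoints.

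A second reply is that section 5.3 collects ventilator status and ICU and hospital stay for the 28-day outcomes, so some changes can be dated. That stands in part: a final liberation from ventilation could be found. But levels 3, 4 and 5 differ by oxygen support, and 6 and 7 by other organ support. The SAP's daily safety outcomes, which include oxygen and vasopressor use, cover only the first five days. Nor does the plan say these sources will feed the scale.

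A third reply is that the footnote is loose wording for daily scoring while hospitalized. That may be so, but it does not say this, and section 5.3 gives a different schedule.

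**Conclusion.** The concern holds in a limited form. As written, patients who are discharged or die on about days 9–13 have no scheduled score from day 8 to exit, and no rule fills those days. The daily displays lack these states. Survivors who first improve in hospital on day 8 or later and go home on days 9–13 are dated at discharge, up to about 5 days late, while the same course in a patient still in hospital on day 14 is dated correctly.

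The share affected is not known. For the displays, 37.5–52% is an upper bound; for the improvement endpoint, removing deaths lowers it to 25–36%, with further unquantified exclusions. Both rest on power-planning distributions, one of them simply uniform, not on forecasts of length of stay.

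Two stronger readings are tempting and unsupported. One is that faster recoverers in general get later event times; anyone who improves on days 1–7 is dated from scheduled scores. The other is that an arm sending more patients home on days 9–13 is penalised; the documents give no basis for the direction or size of a between-arm effect.

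The day-14 primary and day-7 secondary analyses use days scheduled for all patients and are untouched. The displays are descriptive. This is a correction that should be made for a named secondary endpoint; it does not threaten the main result.

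**What to change.** 1. Reconcile Protocol section 5.3 and Appendix 1 to one schedule: every day the patient is hospitalized through day 14, and day 14 on all patients.
2. For patients who left or died before day 14, abstract the inpatient days from day 8 to exit from the medical record.
3. State in the SAP that these scores are used in the daily displays and in the time to a 1-point decrease, and that the post-discharge rule applies to both.
4. Because the endpoint is censored at day 28, either extend the in-hospital abstraction to day 28 or restrict the endpoint to the days scored.

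The cost is protocol, SAP and CRF wording plus modest chart or data-query abstraction: at most six inpatient days (8–13) per affected patient for steps 1–2, and more if step 4 is met by extending to day 28. Section 5.3 already relies on data queries and the medical record, so the abstraction needs no new visit or patient contact.
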